8.2 Procedures

- a) Virtual information session: All potentially eligible and interested participants will first complete this session. At the end of the session, participants will provide verbal informed consent and will be invited to complete the behavioral run-in period.
- b) Behavioral run-in: participants will be emailed a link to a secure Redcap survey and asked to complete the following steps:
 - Electronic consent
 - Survey to determine eligibility
 - Profile with contact information, including correct address to send scale and contact preferences (email or text)
 - Online W9 form to facilitate delivery of incentives
 - Baseline demographic and study specific surveys (see Appendix 5)

Participants will be asked to complete 5 days of food logging. Participants can log food in MyFitnessPal (MFP), a free app for food tracking, and share with research staff or they can keep a food diary on paper and send in screenshots via text or email. Participants who provide informed consent and complete the run-in period will be sent a digital scale along with handouts in preparation for the virtual kick-off session.

- c) Virtual kick-off session: Once participants have received the scale, they will be eligible to sign up for a virtual kick-off session, during which participants will be randomized. Participants can sign up through the study website (via Redcap) or by contacting a CRC. This session will be conducted by research staff over Zoom. Randomization will occur at the beginning of the session and participants will be placed in one of two breakout rooms for the intervention or control arm.

- Control arm: study staff member will inform participants that they are in the control arm.

- Intervention arm: study staff will lead the Weight Loss 101 session. This session will review weight, calorie, and physical activity goals and evidence-based weight loss strategies, including food logging and daily weights. All participants will be asked to lose 10% of their body weight, corresponding to 1-2 lb/week over the 16-week study. Participants will receive a brief introduction to the online BWL study website. The session will also include information about weight loss and exercise while breastfeeding.

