d) Virtual weigh-in: All participants will be asked to complete a virtual weigh-in on the Monday following the kick-off session. Their weight on the Monday morning will serve as their baseline weight for the program. Participants in both arms will be asked to take a photo of the scale with the morning weight and send it to study staff by text or email. The number stays on the scale for 3 seconds after stepping off.

e) Health coach: A study staff member will be trained as a weight loss coach by the PIs. If participants in the intervention arm are having trouble using the platform, reaching their weight loss goals, or have stopped logging into the platform, research staff will reach out to help triage and troubleshoot any barriers.

g) At the end of the 16-week intervention, all participants will be asked to complete their final virtual weigh in and send a photo of the scale to study staff by text or email. At the end of the study, participants will be asked to complete an exit survey. In addition, participants will be offered an opportunity to participate in an online group feedback session on Zoom. Participants will receive \$30 incentive for completing the final weigh-in and exit survey. Study staff will abstract clinically relevant data from the electronic medical record to collect data on demographics, clinical comorbidities, and health care utilization. The collection of these data will obviate the need to further burden participants by asking them additional questions during the survey periods.

9. Analysis plan

Primary outcomes include:

- Enrollment rate, comparing email recruitment strategies (reserved a spot versus commit to health) and comparing mail strategies (mailer versus mailer plus gift)
- Change in weight from baseline to 16-week follow-up
- Proportion of participants losing $\geq 5\%$ of weight

Secondary outcomes:

- Study completion rate between 2 arms
- In the intervention arm, engagement with online BWL platform, including number of total logins, number of weeks with ≥ 1 login, number of weeks that calories, physical activity minutes, and body weight were reported for at least 5 of the 7 days

Exploratory outcomes

- Differences in any of the primary or secondary outcomes according to race/household income

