11.2 Subject confidentiality

Research material will be obtained from participant surveys and clinical data abstracted from the EMR. All participants will provide informed consent for access to these materials. The data to be collected include demographic data (e.g., age, sex, self-identified race) and outcome data. Research material that is obtained will be used for research purposes only. The same procedure used for the analysis of automated data sources to ensure protection of patient information will be used for the survey data, in that patient identifiers will be used only for linkage purposes or to contact patients. The study identification number, and not other identifying information, will be used on all data collection instruments. All study staff will be reminded to appreciate the confidential nature of the data collected and contained in these databases.

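### The end-of-study chart abstraction (section 8.2 g) does not list weight, so a cheap auxiliary variable for missing 16-week weights, possible in both arms, is not planned

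*Combined protocol and SAP*

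**What the plan says.** Section 9 lists weight change to 16 weeks and the proportion losing at least 5% among the primary outcomes. Section 8.2 supplies the data for both.

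- **Arm known first.** Randomization opens the kick-off session and women then learn their arm: "Control arm: study staff member will inform participants that they are in the control arm". The baseline weigh-in is on the following Monday: "Their weight on the Monday morning will serve as their baseline weight for the program".
- **Method.** "Participants in both arms will be asked to take a photo of the scale with the morning weight and send it to study staff". At 16 weeks women are again asked to "complete their final virtual weigh in and send a photo of the scale to study staff".
- **Chart review.** For the end of the study, section 8.2 g) states: "Study staff will abstract clinically relevant data from the electronic medical record to collect data on demographics, clinical comorbidities, and health care utilization". Weight is not named.
- **Access.** Section 11.2 describes survey data and clinical data from the chart, and adds: "All participants will provide informed consent for access to these materials".
- **Other weights.** Section 5.1 asks intervention women to log daily weight on the platform, and section 11.1 lets study staff see those entries. Nothing similar is described for usual care. Section 6 takes pregravid and delivery BMI from the chart, for recruitment screening only.
- **Missing data.** Section 9 states that multiple imputation will be used, with no imputation model or auxiliary variables. Sensitivity analyses are promised but not named.

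**The concern.** The follow-up information is lopsided. An intervention woman who sends no final photo may have left a series of platform weights. A usual-care woman who sends none has only her baseline weight among the trial weights described. With 20 women planned in usual care, each is 5% of that arm (1/20). Imputation for her then rests on baseline weight, arm and whatever covariates are chosen, and it assumes that she resembles women who did send a photo.

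The chart is the one source mentioned in the plan that could supply a follow-up weight by the same route in both arms, and staff will be opening it anyway. If women who stop responding have done worse or better than predicted, a recorded weight carries some of that information into the imputation. Without it, the error in the arm contrast stays in full.

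**Working it through.** **Inputs from the documents.** Section 5.4: 60 randomized, 40 intervention and 20 usual care. The documents give no rate of missing final weights, no SD of weight change and no frequency of clinic weights, so the rates below are assumptions shown as ranges. The plan states no figure on this point to reproduce.

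**1. How many women could contribute.** Assume 20-30% send no final photo and 30-50% of those have a chart weight near week 16.

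- Low: 60 × 0.20 × 0.30 = 3.6
- High: 60 × 0.30 × 0.50 = 9
- Usual care alone: 20 × 0.20 × 0.30 = 1.2 to 20 × 0.30 × 0.50 = 3

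**2. Effect on an arm mean.** Assume women without a photo truly differ by 3 kg from their predicted weight. Error = share missing × (1 − share recovered) × 3 kg.

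| Share missing | None recovered | 30% recovered | 50% recovered |
|---|---|---|---|
| 20% | 0.60 kg | 0.42 kg | 0.30 kg |
| 30% | 0.90 kg | 0.63 kg | 0.45 kg |

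This is a best case: it credits every recovered woman with zero error, as if the clinic weight were the missing value. It also concerns one arm. Equal errors in both arms would cancel in the contrast.

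**3. Does auxiliary use still help?** A simulation used the same rates, clinic-weight noise with SD 1.5-3 kg, and a 3 kg departure among women without a photo in the intervention arm only. Including the chart weight as an auxiliary variable cut the bias in the arm contrast by about 30-55% and slightly lowered the root mean squared error. The top of that range can pass the 50% in step 2 because the imputation model also shifts the predictions for women without a chart weight. The gain shrinks as clinic noise grows relative to the spread of weight change, so 30% is not a floor.

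**4. Could clinic weights test the photo weights?** Apply the same 30-50% to the 70-80% who send a photo. Women with both weights:

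- Intervention: 40 × 0.70 × 0.30 = 8.4 to 40 × 0.80 × 0.50 = 16
- Usual care: 20 × 0.70 × 0.30 = 4.2 to 20 × 0.80 × 0.50 = 8

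Assume an SD of 1.5-3 kg for photo minus clinic weight. The 95% half-width for the difference between arms is 1.96 × SD × √(1/n₁ + 1/n₂):

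- Best: 1.96 × 1.5 × √(1/16 + 1/8) = 1.3 kg
- Worst: 1.96 × 3 × √(1/8 + 1/4) = 3.6 kg

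A differential error below about 1 kg could not be resolved even in the best case. The comparison can be descriptive only.

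**The case against.** The strongest reply is that the plan is silent on weight and does not exclude it. Section 8.2 g) opens with a broad phrase about clinically relevant data, and section 11.2 says that the data collected include outcome data. That stands: weight is unlisted, and the text needs clarifying.

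Three stronger readings are tempting, and the documents do not support them.

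- **That the home weights are never checked.** The photo goes to staff and documents the reading, though not who stood on the scale. Platform weights also exist in the intervention arm. They are self-entered by the same unblinded women, so they are not independent. What can be said is that no independent check is planned.
- **That usable weights are already on record and are being discarded.** No section shows a clinic weight near week 16. Women may enter up to 12 months after delivery, and eligibility requires delivery at the two hospitals, not continuing care there. Such weights may exist for some women; the number, timing and balance between arms are unknown.
- **That chart weights are the only outcome information on women who send no photo.** In the intervention arm, platform logs may be closer in time than any clinic visit.

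It can also be said that access to the chart does not settle consent for this item. That is fair: the consent form was not available for this review.

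The objection that an auxiliary variable cannot deliver the gain mostly fails. The benefit is smaller for each woman than full replacement, but the simulation shows that a useful part of it remains.

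**Conclusion.** The point holds as a cheap improvement to a pilot. Both weight outcomes depend on unblinded home photos, usual care has no other described follow-up weight, and the planned chart review does not list the one item that could inform imputation in both arms.

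The likely yield is small: about 4-9 of 60 women, with at best a fall in arm-mean error from 0.60-0.90 kg to 0.30-0.63 kg. These figures rest on assumed rates of missing photos (20-30%) and chart weights (30-50%) and on an assumed 3 kg departure. None of these is in the documents. If few women have a clinic weight near week 16, the gain is close to nothing.

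The case rests on the auxiliary use. A reader might infer that clinic weights would also expose biased self-measurement between arms, but at this size the comparison is too imprecise to do so.

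**What to change.** 1. In section 8.2 g), add to the abstraction form for both arms every recorded weight with its date, from baseline to about 6 weeks after week 16.
2. In section 9, name the chart weight nearest week 16 as an auxiliary variable in the multiple imputation for women with no final photo. Platform weights may be added for the intervention arm. State that neither replaces the photo weight as the outcome, and fix the window and selection rule before the arm codes are opened.
3. Report by arm how many women have a chart weight, with and without a final photo. Present any photo-minus-clinic difference by arm as descriptive, with no test.
4. Confirm that the consent wording covers recorded weights. If they will not be used, say why.

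The cost is one dated field in a chart review already planned, with no added burden on participants. Clinic scales, clothing and timing differ from the home weigh-in, and women with visits are a selected group. For those reasons the weight should serve only as auxiliary information.

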Two-thirds of women have overweight or obesity, and women of reproductive age have experienced the greatest increase in obesity rates of any group.(1) Obesity during reproductive years is a risk factor for pregnancy complications and higher risk of mortality later in life.(2) Women with cardiovascular (CV) risk factors, such as hypertension (HTN) or diabetes (DM) are at higher risk of obesity-related CV complications, as are women with pregnancy complications such as gestational hypertension, preeclampsia, and diabetes. The Diabetes Prevention Program (DPP) is an intensive in-person program resulting in sustained weight loss.(3,4) Behavioral weight loss (BWL) programs modeled after DPP and adapted to online platforms have shown success in different settings. An online behavioral weight loss program modelled after the DPP may be attractive to postpartum women, who may have difficulty attending in-person sessions due to competing demands of caring for a newborn.(5) The objective of this study is to use a randomized clinical trial to test the feasibility and effectiveness of a 16-week online behavioral weight loss program compared to usual care to promote weight loss in the postpartum period among women with CV risk factors. We will also be testing different behavioral strategies to recruit postpartum women to the study. We will be partnering with collaborators at the University of Connecticut (UConn) who have extensively evaluated this platform in different populations.

2. Overall objectives

The objective of this study is to evaluate the feasibility of an online behavioral weight loss program on weight loss among postpartum women at increased cardiovascular risk. A secondary objective is to evaluate the effectiveness of different behavioral strategies to recruit a diverse population of women to enroll in the study.

3. Aims

3.1 Aim 1: To understand feasibility and compare weight loss between postpartum women participating in an online behavioral weight loss intervention compared to usual care.

3.2 Aim 2: To compare recruitment and enrollment strategies in enrolling postpartum women in a weight loss intervention.

4. Background

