5.1 Design

We will conduct a pilot two-arm randomized, controlled trial comparing the effect of an online BWL program (intervention) to usual care on weight loss after 16 weeks. The enrollment process and intervention will all be conducted remotely. All interested participants will be asked to complete a 7-day run-in period during which time they will complete surveys and submit a daily food log. Participants will be randomized 2:1 into the intervention and control arms, respectively. At the end of the 16-week intervention, participants will be asked to complete end-of-study surveys and complete an end-of-study virtual weigh-in.

Study population

We will recruit women who have recently delivered at the Hospital of the University of Pennsylvania or Pennsylvania Hospital. We will recruit women who are 6 weeks – 12 months postpartum at the time of study recruitment and have ≥ 1 CV risk factor.

Trial arms

Arm 1. Usual care: Participants will receive educational resources on weight loss and a digital scale.

Arm 2. Online behavioral weight loss: Participants will receive educational resources on weight loss and a digital scale. Participants will participate in a “Weight Loss 101” virtual session, where they are introduced to successful components of weight loss. They will be enrolled in a 16-week online program that is based on the Diabetes Prevention Program (DPP) and involves weekly brief videos, a self-monitoring platform, and automated feedback.(3,6–8)

Intervention

Participants in all arms will attend a virtual Information session, undergo a 1-week behavioral run-in period, and attend a virtual Kick-off session. (see Study Schema). After completing these steps, all participants will be asked to complete a virtual weigh-in at the start and end of the 16-week intervention. In addition, the intervention arm will receive:

- a. Weight loss and physical activity goals as part of the Weight Loss 101 session. All participants will be asked to lose 10% of their body weight, corresponding to 1-2 lb/week over the 16-week study. Participants will be enrolled in the online behavioral weight loss program. The program involves the following components and described in more detail in Appendix 1:
- b. Weekly multimedia videos (lesson plan): These illustrated videos are < 5 minutes in length and include topics such as stimulus control, goal setting, and problem solving.

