To compare sample characteristics between arms we will use t-tests or Wilcoxon rank-sum tests for continuous variables and Pearson chi square tests or Fisher's exact tests for categorical variables. Generalized linear mixed effects models will be used to assess for differences in weight, given repeated observations. We will use fixed effects to adjust for study arm, baseline weight, and calendar month, which may reflect seasonal variations that make weight loss harder or easier. We will conduct a number of sensitivity analyses to evaluate the robustness of our findings. All hypothesis tests will be two-sided using a two-sided alpha of 0.05 as our threshold for statistical significance. We will use Stata and/or SAS to analyze the data. We will use multiple imputation for missing data.

10. Investigators

[name], MPH is the co-Principal Investigator (PI) and is an Assistant Professor of Medicine at the Perelman School of Medicine. She is Director of the Women's Cardiovascular Health Program. She has experience running lifestyle interventions among postpartum women.

[name] is the co-Principal Investigator (PI) and is a Professor of Psychology in Psychiatry at the Perelman School of Medicine. She is Director of the Center for Weight and Eating Disorders. She has extensive experience designing and running behavioral weight loss clinical trials.

[name] is a co-investigator. She is Associate Professor in the Department of Allied Health Sciences and Co-Director of the Weight Management Research Group at the University of Connecticut (UConn). She developed the online BWL platform along with collaborators at the University of North Carolina.

The Clinical Research Coordinator has experience with administering studies involving interventions with pregnant and postpartum populations and also has experience training Research Assistants to follow study protocols.

11. Human research protection

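### The weight model in section 9 does not say which weigh-ins are the response or name a week-16 contrast; fitted as listed to both weigh-ins, its arm term is about half the 16-week difference

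*Combined protocol and SAP*

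**What the plan says.** Section 5.1 describes a trial "comparing the effect of an online BWL program (intervention) to usual care on weight loss after 16 weeks". Section 9 lists among the primary outcomes "Change in weight from baseline to 16-week follow-up". The model for weight follows in two sentences of the same section: "Generalized linear mixed effects models will be used to assess for differences in weight, given repeated observations", and then "We will use fixed effects to adjust for study arm, baseline weight, and calendar month". Random effects, covariance structure and response rows are not given. Missing data are to be multiply imputed.

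On measurement, section 5.1 says that "all participants will be asked to complete a virtual weigh-in at the start and end of the 16-week intervention". Section 8.2(d) defines the first of these as the baseline: "Their weight on the Monday morning will serve as their baseline weight for the program". Section 8.2(g) gives the second: "all participants will be asked to complete their final virtual weigh in and send a photo of the scale to study staff". The only other weights collected repeatedly are the daily entries on the online platform (section 5.1, intervention item c). Section 11.4 confirms that only the intervention group is enrolled on that platform.

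**The concern.** The outcome is a single difference per woman, baseline to week 16. The model is justified by repeated measurement, yet the two arms share only two weights, and one of them is already a covariate. The text leaves open what the repeated rows are and which coefficient answers the question.

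This matters because the opening section says the trial will "test the feasibility and effectiveness of a 16-week online behavioral weight loss program compared to usual care to promote weight loss", and section 4 adds a preliminary efficacy comparison with usual care. In a pilot of 60 women, the between-arm difference in kg and its confidence interval are main products, and a later trial may be planned on them. Two analysts following section 9 could report estimates that differ by a factor of two. The p-value would give little warning, because the standard error shrinks along with the estimate.

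**Working it through.** **Inputs from the documents.** 60 women randomized 2:1, so 40 and 20 (section 5.4); two weigh-ins per woman, Y0 and Y16 (sections 5.1 and 8.2); listed terms arm, Y0 and calendar month (section 9); two-sided alpha 0.05. The plan gives no effect size, SD or power for weight, so there is no figure of its own to reproduce. Effects and SDs below are assumptions.

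**1. Both weigh-ins as response rows, no month-of-measurement term.** Each woman contributes two rows with the same covariates (1, arm, Y0). With complete data and a random intercept, the fixed effects equal those from regressing her mean, (Y0 + Y16)/2, on those covariates. Regression coefficients are linear in the response, so

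arm coefficient = ½ × [arm coefficient for Y0 given Y0] + ½ × [arm coefficient for Y16 given Y0] = ½ × 0 + ½ × d = d/2,

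where d is the week-16 ANCOVA difference. This does not depend on SD or correlation. It holds within each completed data set under multiple imputation, and hence for the pooled estimate. A visit main effect alone does not change it, because visit is balanced within each arm. Start month, being constant within a woman, does not change it either.

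**2. Numerical check** (40 v 20, SD of change 5 kg, baseline SD 18 kg, 5,000 trials per row, least squares):

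| True difference (kg) | Listed terms, both weigh-ins | Week-16 ANCOVA |
|---|---|---|
| −2 | −1.02 | −2.03 |
| −4 | −2.00 | −4.01 |
| −6 | −3.00 | −5.99 |

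The largest departure from exactly one half in any trial was about 3 × 10⁻¹⁴. Random-intercept REML fits agree: for a true −4 kg, −2.01 against −4.01 (60 trials).

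**3. With calendar month of measurement.** Month now differs between a woman's two rows, so step 1 no longer applies exactly. With 16 weeks taken as 112 days, calendar months, 122-day enrolment, a true −3 kg and SD 4.5 kg, the ratio of the stacked to the ANCOVA coefficient had median 0.498 and a central 95% range of 0.34 to 0.66 (2,000 trials). It is half on average, not half in each trial.

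**4. Missing and not imputed.** With 20% of week-16 weights missing, the stacked coefficient was −1.67 against −3.69 with month (1.67/3.69 = 0.45) and −1.89 against −4.26 without (1.89/4.26 = 0.44).

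**5. Effect on the test.** For a true −4 kg, SD 5 kg and no month, estimate over standard error is 2.007/0.763 = 2.63 stacked and 4.014/1.380 = 2.91 for ANCOVA. Simulated type I error was 4.1–6.2% stacked and 4.0–6.4% ANCOVA. Power at −3 kg and SD 4.5 kg was 67% v 66% with month of measurement, 58% v 66% with no month and 56% v 64% with start month. The largest gap found was 52% v 65% (−2 kg, SD 3 kg, start month).

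**6. Week 16 (or change) as the only response.** The listed terms give d directly. Each woman then has one row, so there are no repeated observations and the model is ANCOVA.

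**7. Daily platform weights as the repeated rows.** Usual care has no such series, so these weights cannot supply a between-arm comparison of repeated observations.

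**The case against.** The best defence is that section 9 is a summary. It omits random effects, covariance and the imputation model as well, so the absence of an arm-by-visit term is weak evidence that one would be left out. Read beside the outcome definition, a list that adjusts for baseline weight points naturally to week 16 or change as the response, with the mixed-model label used loosely. The stacked fit is also awkward enough to draw attention: half its responses equal a covariate, and in a check of 200 REML fits the random-intercept variance was essentially zero, with boundary warnings in 100 and non-convergence messages in 126. Finally, this is a pilot, and the test is not badly damaged.

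Most of that stands as a limit on the point. It does not remove it. These sentences are the only specification of the weight model; taken literally, they lead to the halved coefficient; and the reading that avoids it has to set aside the stated reason for using a mixed model. Software warnings vary and do not replace a stated contrast.

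A reader might infer that the trial will report half the true effect. The documents do not support that, because they never say that both weigh-ins are response rows or that the listed terms are the whole formula. A reader might also infer that the ratio is exactly one half in every analysis. Step 3 shows that it is not once month of measurement is included.

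**Conclusion.** The point holds in conditional form and should be fixed. The response rows and the week-16 contrast are unspecified, and the stated model does not match the stated outcome. If the listed terms are fitted to both weigh-ins, the reported difference is exactly half the week-16 effect with complete or imputed data and no month-of-measurement term, and about half on average with one. The factor of one half does not depend on assumed effects or SDs.

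The harm is to the estimate in kg and to its interval, which would be centred in the wrong place. How often that interval misses the true difference depends on values the plan does not give. As illustration only, at −3 kg and SD 4.5 kg the nominal 95% interval covered the true value in 38–45% of simulated trials, against 94–96% for ANCOVA across the scenarios run. Type I error stays near 5%, and power changes little at the main assumption. The proportion losing at least 5% of weight and the enrollment outcomes are not affected. Confidence is medium, because which analysis is intended cannot be settled from the text.

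**What to change.** Replace the two model sentences in section 9 with one of the following.

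- **ANCOVA.** Response: the week-16 weigh-in (or change from baseline). Terms: arm and baseline weight. Calendar month may be kept, but say whether it is start month or month of measurement. The effect is the arm coefficient.
- **Two-visit mixed model.** Responses: both weigh-ins. Terms: visit and arm-by-visit, with the arms constrained equal at baseline and baseline weight not also a covariate. The effect is the week-16 arm contrast. A visit main effect alone is not enough.

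In either case, state that the intervention-only platform weights are not used in the between-arm model.

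The cost is wording: no new data, visits or participants. Compared like for like (no month, SD 4.5 kg, 2,000 trials), the two options perform alike. At −3 kg both estimate −3.03 kg, with coverage 94.5% (two-visit) v 94.9% (ANCOVA) and power 68% v 67%; type I error is 5.7% v 5.1%.
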